9.2 Safety Event Reporting Procedures

9.2.1 Reporting Procedures for Adverse Events and Adverse Device Effects That do not Meet Serious Criteria

The investigator is responsible for ensuring that all adverse events **and adverse device effects (including the OLTP and CHU substudy)** observed by the investigator or reported by the subject that occur after the first dose of investigational product through the end of the safety follow-up visit (16 weeks after the last dose of investigational product) are reported using the Event CRF (eg, Adverse Event Summary), including events that are reported to the Event Adjudication Committee for adjudication.

The investigator must assign the following adverse event attributes:

- adverse event diagnosis or syndrome(s), if known (if not known, signs or symptoms),
- dates of onset and resolution (if resolved),

- severity and/or toxicity,
- assessment of relatedness to investigational product (**AMG 334/placebo**), and/or **the Amgen medical devices (pre-filled syringe or the AI/Pen)**, and/or **study-mandated procedure/study activity**, and
- action taken.

The adverse event grading scale used will be the CTCAE. The grading scale used in this study is **available at the following location:**

http://ctep.cancer.gov/protocolDevelopment/electronic_applications/ctc.htm.

During the double-blind treatment period, the investigator must assess whether the adverse event is possibly related to the investigational **medicinal** product (**AMG 334/placebo**). This relationship is indicated by a “yes” or “no” response to the question: “Is there a reasonable possibility that the event may have been caused by the investigational **medicinal** product (**AMG 334/placebo**)?”

During the OLTP and the CHU substudy, the investigator must assess whether the adverse event is possibly related to **AMG 334**. This relationship is indicated by a “yes” or “no” response to the question: “Is there a reasonable possibility that the event may have been caused by **AMG 334**?”

During the OLTP and the CHU substudy, the investigator must assess whether the adverse event is possibly related to the prefilled syringe or AI/Pen (investigational medical devices used to administer **AMG 334**). The relationship is indicated by a “yes” or “no” response to the question: Is there a reasonable possibility that the event may have been caused by the investigational medical devices?

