The investigator must assess whether the adverse event is possibly related to any study-mandated activity (eg, administration of investigational product, protocol-required therapies, device(s) and/or procedure (including any screening procedure(s))). This relationship is indicated by a “yes” or “no” response to the question: “Is there a reasonable possibility that the event may have been caused by a study activity (eg, administration of investigational product, protocol-required therapies, device(s)), and/or procedure”?

Relatedness means that there are facts or reasons to support a relationship between investigational product and the event.

The criteria for grade 4 in the CTCAE grading scale differ from the regulatory criteria for serious adverse events. It is left to the investigator's judgment to report these grade 4 abnormalities as serious adverse events.

If the severity of an adverse event changes from the date of onset to the date of resolution, record as a single event with the worst severity on the Adverse Event Summary CRF.

The investigator is responsible for reviewing laboratory test results, ECGs, and vital signs and determining whether an abnormal value in an individual study subject represents a clinically significant change from the subject's baseline values. In general, abnormal laboratory values, ECG findings, or vital signs without clinical significance (based on the investigator's judgment) are not to be recorded as adverse events. However, laboratory values, ECG findings, or vital signs that require treatment or adjustment in current therapy are considered adverse events. Where applicable, clinical sequelae (not the laboratory abnormality or ECG abnormality) are to be recorded as the adverse event.

The investigator is expected to follow reported adverse events until stabilization or reversibility.

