Appendix B. Sample Serious Adverse Event Contingency Report Form

Completion Instructions - Electronic Adverse Event Contingency Report Form (For use for clinical trial studies using Electronic Data Capture [EDC])

NOTE: This form is to be used under restricted conditions outlined on page 1 below. If you must fax an event report to Amgen, you must also enter that event into the EDC system (eg, Rave) when it becomes available.

General Instructions

The protocol will provide instruction on what types of events to report for the study. This form is to be used **ONLY** to report events that must be captured in the Amgen safety database. *Indicates a mandatory field.

Types of Events to be reported on this form

- Serious Adverse Events (regardless of causal relationship to IP)

1. Site Information

Site Number* – Enter your assigned site number for this study

Investigator*, Country*, Reporter*, Phone No., and Fax No. – Enter information requested

2. Subject Information

Subject ID Number* – Enter the entire number assigned to the subject

Age at event onset, Sex, and Race – Enter the subject's demographic information

End of Study date – If the subject has already completed the study or terminated the study early, enter the End of Study date

If you are submitting follow-up information to a previous report, provide the serious adverse event term for the previous report as well as the start date for the initial event.

3. Serious Adverse Event

Provide the date the Investigator became aware of this information

Serious Adverse Event Diagnosis or Syndrome* –

- If the diagnosis is known, it should be entered. Do not list all signs/symptoms if they are included in the diagnosis.
- If a diagnosis is not known, the relevant signs/symptoms should be entered.
- If the event is fatal, the cause of death should be entered and autopsy results should be submitted, when available.

Date Started* – Enter date the adverse event first started (not the date on which the event met serious criteria) rather than the date of diagnosis or hospitalization. **This is a mandatory field.**

Date Ended – Enter date the adverse event ended and not the date when the event no longer met serious criteria. If the event has not ended at the time of the initial report, a follow-up report should be completed when the end date is known. If the event is fatal, enter the date of death as the end date.

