Open-label Treatment Phase	Week 28	
• The 1st OL dose day	
• Week 28 dose date-1• OLTP day 28 if Week 28 dose is not received (either missed or IP discontinued prior to Week 28)

	Week 32 or later when eDiary is used	
• Same rule as above	
--	--------------------------------------	--	--

Study Visit

Since the actual visit for a subject may not exactly coincide with their targeted visit date, the actual visit date is mapped to the study visit as follows.

Study Visit	Target Day	Study Day
Baseline		Please refer to Section 6.3 Baseline Assessment of the Study
Day 1	1	1
Week 4	29	16-43
Week 8	57	44-71
Week 12	85	72-99
Week 16	113	100-127
Week 20	141	128-155
Week 24	169	
• 156 to (week 24 OLTP dose date – 1) for subjects who receive OLTP dose at week 24• 156-183 for subjects who did not receive OLTP dose at week 24
Week 28	197	
• Week 24 OLTP dose date to 211 for subjects who receive OLTP dose at week 24• 184-211 for subjects who received at least one OLTP dose and did not

		receive OLTP dose at week 24 (e.g., first OLTP dose was postponed)
Week 32	225	212-239
Week 36 to Week 72	Following same monthly windowing as Week 32	
Safety follow-up	Based on visit name from RAVE or other source data	

Note:

If more than one visit (including the unscheduled visits, ie, CPEVENT = 'UNSCHED') fall within the same defined window, scheduled visit will be used regardless of the distance from the target day. Unscheduled visit will only be used when there is no scheduled visit in the defined window. The closest visit to the target day among the same type of visit (scheduled vs. unscheduled) will be considered for analysis. If two assessment dates are equidistant from the target date, the latter visit will be considered for analysis.

For safety analyses which are summarized by study phase, analysis windows will be set up based on study phase:

Study Phase	Start Time Point	End Time Point
Double-Blind Treatment Phase	Study Day 1 after the 1 st DB IP Dose	
First OL Dose Date for subjects who receive OL IP dose;Min(EOS Date, last IP dose date + 112 days) for subjects who do not receive any OL IP dose
Open-Label Treatment Phase	1 st OL IP Dose Date	Min(EOS Date, last OL IP dose date + 112 days)

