10.6.1 Adverse Events

The Medical Dictionary for Regulatory Activities (MedDRA) version 18 or later will be used to code all adverse events (AE) to a system organ class and a preferred term. All adverse events will be graded using the Common Terminology Criteria for Adverse Events (CTCAE) Version 4. All adverse event tables will be summarized by treatment group. Refer to [Section 6.1.2](#) for the definition of treatment-emergent adverse event.

The subject incidence of AEs will be summarized for all treatment-emergent AEs (TEAEs), serious AEs, AEs leading to withdrawal of investigational product, fatal AEs, and device-related AEs for DBTP and OLTP, respectively.

Subject incidence of all treatment-emergent AEs, serious AEs, AEs leading to withdrawal of investigational product, serious AEs leading to withdrawal of investigational product, fatal AEs and device-related AEs will be tabulated by system organ class in alphabetical order and preferred term in descending order of frequency, for DBTP and OLTP, respectively.

In addition, subject incidence of all treatment-emergent AEs and serious AEs will be tabulated by system organ class in alphabetical order, preferred term and CTCAE grade in descending order of frequency, for DBTP and OLTP, respectively. Subject incidence of all treatment-emergent AEs and serious AEs will also be tabulated by preferred term in descending order of frequency.

Treatment-related treatment-emergent AEs will be summarized for OLTP by system organ class, preferred term and CTCAE grade.

In addition, exposure-adjusted incidence rate will be produced for DBTP and OLTP, respectively. All treatment-emergent AEs and serious AEs will be tabulated by preferred term in descending order of frequency.

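### An adverse event that worsens after the first open-label dose keeps one record at its worst grade, so, read by onset date, that grade is shown in the double-blind tables, including the placebo column

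*Protocol*

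**What the plan says.** **Recording.** In Protocol 9.2.1, if the grade of an event "changes from the date of onset to the date of resolution, record as a single event with the worst severity". The attributes the investigator must assign include onset and, where it applies, resolution dates; no date of grade change is listed. Follow-up does not stop at a phase boundary: "The investigator is expected to follow reported adverse events until stabilization or reversibility". For serious events, the Appendix B form instructions for the start date read "Enter date the adverse event first started (not the date on which the event met serious criteria) rather than the date of diagnosis or hospitalization".

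**Analysis.** SAP 6.1.2 classes an event as treatment-emergent by whether it started before the first dose; worsening is not a criterion. SAP 6.4 states "For safety analyses which are summarized by study phase, analysis windows will be set up based on study phase". The double-blind window ends at the first open-label dose date for subjects who receive one, and the open-label window starts on that same date. In SAP 10.6.1, for each phase, "subject incidence of all treatment-emergent AEs and serious AEs will be tabulated by system organ class in alphabetical order, preferred term and CTCAE grade". Protocol 10.5.5 likewise requires safety to be analysed separately for the two phases.

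**Treatment change.** Subjects from every randomized arm who enter the open-label phase receive AMG 334, including those who had placebo. Entry is conditional (Protocol 7.2.24): the subject must have completed the double-blind phase without ending product early, still consent, and be appropriate for continued treatment.

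**The concern.** The recording rule treats an event as one object from onset to resolution, while the analysis cuts time at the first open-label dose. The two conflict for an event that spans the cut. Its worst grade may have arisen on open-label drug, but the record has only an onset date before the cut and a resolution date after it.

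The double-blind phase is the only placebo-controlled safety comparison in the trial. Severity that developed on AMG 334 in a former placebo subject would be shown against placebo and would be missing from the open-label tables, where a reader would look for it. Two further outputs can be affected. The open-label table of treatment-related events by grade has no separate entry for the worsening. If a late-serious event is dated to its mild onset, the exposure-adjusted serious-event rates (SAP 6.6 and 10.6.1) also give it the wrong phase and the wrong time at risk.

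**Working it through.** The plan states no figure for this, so the check follows one record through the rules and then gauges size.

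**Tracing one event.** A placebo subject has a grade 1 event from week 22. It is unresolved at the first open-label dose at week 24 and reaches grade 3 at week 30.

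1. Protocol 9.2.1: one record, onset week 22, grade 3.
2. SAP 6.1.2: it started after the first double-blind dose, so it is treatment-emergent.
3. SAP 6.4: week 22 lies in the double-blind window. The date of grade 3 is not among the listed attributes, so it cannot be set against the windows.
4. SAP 10.6.1: it is counted as grade 3 in the double-blind placebo column. With no onset in the open-label window, it is not an open-label event.

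**Looking for a rule that corrects this.** Protocol 9.1.1 counts worsening of a pre-existing condition as an adverse event, but for an event already on record the single-record instruction is the specific one. SAP 6.1.2, 6.4 and 10.6.1 contain no rule for worsening after the switch. SAP Section 11 lists no departures from the protocol.

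**Size.** Inputs from the documents: about 131 placebo subjects (Protocol 3.4), 66 in the 28 mg arm, and 63.0% of placebo subjects with a treatment-emergent event in the global Phase 3 episodic migraine study (Protocol 2.3). Two inputs are assumptions: the share of those subjects with an event ongoing at the first open-label dose (5% to 20%) and the share of these that then worsen (2% to 20%).

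One subject moves an arm by 100/131 = 0.76 percentage points, or 100/66 = 1.52 points in the 28 mg arm.

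Placebo subjects affected = 131 × 0.63 × ongoing share × worsening share = 82.5 × ongoing share × worsening share:

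| Ongoing | 2% worsen | 5% worsen | 10% worsen | 20% worsen |
|---|---|---|---|---|
| 5% | 0.08 | 0.21 | 0.41 | 0.83 |
| 10% | 0.17 | 0.41 | 0.83 | 1.65 |
| 20% | 0.33 | 0.83 | 1.65 | 3.30 |

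The range is 0.08 to 3.3 subjects, or 0.06 to 2.5 points. It applies the shares to all 131 placebo subjects, although not all enter the open-label phase, so for any given pair of shares it errs high.

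**The case against.** The strongest reply is that this concerns tabulation, in a few subjects, under rules that are partly inferred. Much of that stands.

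- **Phase by onset is not written down.** SAP 6.4 gives windows but does not say which event date is compared with them. Onset is the natural reading, and no other allocation rule is given, but it is a reading.
- **Seriousness rests on weaker text.** Section 9.2.1 is headed for events that do not meet serious criteria, and 9.2.2 does not repeat the single-record rule. The start-date instruction in Appendix B belongs to a contingency form for when electronic capture is unavailable. Against that, 9.2.2 requires serious-event information to be consistent with the CRF, and SAP 6.1.2 takes seriousness from one flag on the adverse event page. Late-serious events are therefore probably treated the same way, but this is not established.
- **The eCRF is not among the documents.** It may capture more dates than 9.2.1 lists.
- **Not every placebo subject switches.** A reader might infer that all do at week 24. The entry conditions in 7.2.24 rule that out, and subjects with the most troubling events may be the least likely to enter.
- **Oversight is not impaired.** New information on a serious event must reach the sponsor within 24 hours, and relatedness to AMG 334 is assessed in the open-label phase.
- **A forced split has its own cost.** Opening a new event at every worsening counts continuing events twice, including in subjects who stayed on AMG 334.

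None of this supplies a rule that puts later worsening in the phase where it occurred.

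**Conclusion.** The point holds in limited form. Followed as written, and with phase taken from onset date, the plan shows worsening after the first open-label dose as double-blind severity and leaves it out of the open-label tables. Only events that start double-blind and are unresolved at the first open-label dose are affected. Any-grade double-blind incidence does not change, and SAP 10.6 plans no testing between arms.

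Roughly 0.1 to 3 placebo subjects would have any worsening. This rests on assumed shares and on a placebo event rate from another study. Severity can be inflated in any arm, so the net effect on the comparison with placebo cannot be signed from the documents.

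Three stronger readings are not supported:

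- The count should not be set against the roughly 2.9 placebo subjects expected to have a serious event (2.2% of 131, using the Phase 3 rate). It covers any grade worsening, and a move from grade 1 to grade 2 is not a serious event.
- A reader might infer that the double-blind grade tables will differ between the primary and final analyses. They may, if regenerated; Protocol 10.4.4 does not clearly say that they will be. The primary analysis is itself exposed, because it waits for the last subject to reach week 24, when earlier subjects may already be on open-label drug.
- Double-blind events could be followed for as long as 112 − 24 = 88 weeks beyond that phase only at the final analysis and on the Amendment 2 timeline. The SAP describes a study ending at week 88, which gives 64 weeks.

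The change is worth making because the date of worsening cannot be recovered from a record that holds only onset and resolution.

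**What to change.** **Protocol 9.2.1 and the CRF completion guideline.** For an event ongoing at the first open-label dose, record its grade at that dose and the date and grade (or seriousness) of any later worsening. A new record opened at the worsening and linked to the first would also serve. Capturing the date and grade is preferable, because it avoids a forced second event.

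**SAP 6.4 and 10.6.1.** State which event date determines phase. Report double-blind grade and seriousness as the worst before the first open-label dose. Count later worsening in the open-label phase. Assign the first open-label dose date to one phase only, since it now ends one window and starts the other.

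**Cost.** One CRF instruction with a few extra fields for events that span the switch, and a few lines in the SAP. Some continuing events will appear in both phases, each at the grade that phase produced; a table footnote can say so.

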9.2.2 Reporting Procedures for Serious Adverse Events

The investigator is responsible for ensuring that all serious adverse events (**this includes the CHU substudy**) observed by the investigator or reported by the subject that occur after signing of the informed consent through the end of the safety follow-up visit (16 weeks after the last dose of investigational product) are recorded in the subject's medical record and are submitted to Amgen, including serious adverse events that are reported to the Event Adjudication Committee for adjudication. All serious adverse events must be submitted to Amgen within 24 hours following the investigator's knowledge of the event via the applicable CRF.

If the electronic data capture (EDC) system is unavailable to the site staff to report the serious adverse event, the information is to be reported to Amgen via an electronic Serious Adverse Event (eSAE) Contingency Report Form within 24 hours of the investigator's knowledge of the event. See [Appendix B](#) for a sample of the Serious Adverse Event Worksheet/electronic Serious Adverse Event Contingency Report Form. For EDC studies where the first notification of a Serious Adverse Event is reported to Amgen via the eSerious Adverse Event

Contingency Report Form, the data must be entered into the EDC system when the system is again available.

During the double-blind treatment period, the investigator must assess whether the serious adverse event is possibly related to the investigational medicinal product (AMG 334 / placebo). This relationship is indicated by a “yes” or “no” response to the question: “Is there a reasonable possibility that the event may have been caused by the investigational medicinal product (AMG 334 / placebo)?”

During the OLTP and the CHU substudy, the investigator must assess whether the serious adverse event is possibly related to AMG 334. This relationship is indicated by a “yes” or “no” response to the question: “Is there a reasonable possibility that the event may have been caused by AMG 334?”

During the OLTP and the CHU substudy, the investigator must assess whether the serious adverse event is possibly related to the prefilled syringe or AI/Pen (investigational medical devices used to administer AMG 334). The relationship is indicated by a “yes” or “no” response to the question: Is there a reasonable possibility that the event may have been caused by the investigational medical devices?

The investigator must assess whether the serious adverse event is possibly related to any study-mandated activity (eg, administration of investigational product, protocol-required therapies, device(s) and/or procedure (including any screening procedure(s))). This relationship is indicated by a “yes” or “no” response to the question: “Is there a reasonable possibility that the event may have been caused by a study activity (eg, administration of investigational product, protocol-required therapies, device(s)), and/or procedure”?

Relatedness means that there are facts or reasons to support a relationship between investigational product and the event.

The investigator is expected to follow reported serious adverse events until stabilization or reversibility.

New information relating to a previously reported serious adverse event must be submitted to Amgen. All new information for serious adverse events must be sent to Amgen within 24 hours following knowledge of the new information. The investigator may be asked to provide additional follow-up information, which may include a discharge summary or extracts from the medical record. Information provided about the serious

adverse event must be consistent with that recorded on the applicable CRF (eg, Adverse Event Summary CRF).

If a subject is permanently withdrawn from protocol-required therapies because of a serious adverse event, this information must be submitted to Amgen.

To comply with worldwide reporting regulations for serious adverse events, the treatment assignment of subjects who develop serious, unexpected, and related adverse events may be unblinded by Amgen before submission to regulatory authorities. Investigators will receive notification of related serious adverse events reports sent to regulatory authorities in accordance with local requirements.

Amgen will report serious adverse events and/or suspected unexpected serious adverse reactions as required to regulatory authorities, investigators/institutions, and IRBs in compliance with all reporting requirements according to local regulations and good clinical practice.

The investigator is to notify the appropriate IRB of serious adverse events occurring at the site and other adverse event reports received from Amgen, in accordance with local procedures and statutes.

